10.6.2. Study Population

Demographics

Age

- GSK standard IDSL algorithms will be used for calculating age using date of the screening visit relative to birth date, where birth date is imputed as:
 - Any subject with a missing date and month will have this imputed as ‘30th June’.
 - Birth date will be presented in listings as ‘YYYY’.

Body Mass Index (BMI)

- Calculated as **Weight (kg) / [Height (m)]²**

Extent of Exposure

- Number of days of exposure to study drug will be calculated based on the formula:
Duration of Exposure in Days = Treatment Stop Date – (Treatment Start Date) + 1

10.6.3. Safety

ECG Parameters
RR Interval

 IF RR interval (msec) is not provided directly, then RR can be derived as : 
 [1] If QTcB is machine read & QTcF is not provided, then : $RR = [(QT/QTcB)^{(2)}] * 1000$ [2] If QTcF is machine read and QTcB is not provided, then: $RR = [(QT/QTcF)^{(3)}] * 1000$
Corrected QT Intervals

 When not entered directly in the eCRF, corrected QT intervals using Bazett’s (QTcB) and Fredericia’s (QTcF) formulas will be calculated, in msec, depending on the availability of other measurements. IF RR interval (msec) is provided then missing QTcB and/or QTcF will be derived as : $QT_{cB} = \frac{QT}{\sqrt{\frac{RR}{1000}}} \qquad QT_{cF} = \frac{QT}{\sqrt[3]{\frac{RR}{1000}}}$

Laboratory Parameters

 If a laboratory value which is expected to have a numeric value for summary purposes, has a non-detectable level reported in the database, where the numeric value is missing, but typically a character value starting with ‘<x’ or ‘>x’ (or indicated as less than x or greater than x in the comment field) is present, the number of significant digits in the observed values will be used to determine how much to add or subtract in order to impute the corresponding numeric value. 
 Example 1: 2 Significant Digits = ‘< x ‘ becomes x – 0.01 Example 2: 1 Significant Digit = ‘> x’ becomes x + 0.1 Example 3: 0 Significant Digits = ‘< x’ becomes x – 1

10.7. Appendix 7: Premature Withdrawals & Handling of Missing Data

10.7.1. Premature Withdrawals

Element	Reporting Detail
General	All subjects who withdraw prematurely from the study/study drug will be documented, listed with the reason for their withdrawal recorded in the final Clinical Pharmacology Study Report (CPSR).

10.7.2. Handling of Missing Data

Element	Reporting Detail
General	Missing PK and safety data will not be imputed
Outliers	Any subjects excluded from the summaries and/or statistical analyses will be documented and flagged in the dataset and listing along with the reason for exclusion in the clinical study report.

10.7.2.1. Handling of Missing Dates

Element	Reporting Detail
General	Partial dates will be displayed as captured in subject listing displays.
Adverse Events	
The eCRF allows for the possibility of partial dates (i.e., only month and year) to be recorded for AE start and end dates; that is, the day of the month may be missing. In such a case, the following conventions will be applied for calculating the time to onset and the duration of the event:
 
 ○ Missing Start Day: First of the month will be used unless this is before the start date of study treatment; in this case the study treatment start date will be used and hence the event is considered On-treatment as per Appendix 4: Treatment States and Phases. ○ Missing Stop Day: Last day of the month will be used, unless this is after the stop date of study treatment; in this case the study treatment stop date will be used. ○ Completely missing start or end dates will remain missing, with no imputation applied. Consequently, time to onset and duration of such events will be missing.

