On Day 15 following the completion of the required Day 14 safety assessments and PK collection, subjects will proceed to Period 2, where site staff will administer a single dose of RBT 300 mg and a single dose of CAB 30 mg in the unit. Subjects will be discharged and dispensed a bottle of RBT and a bottle of CAB to be taken at home on Days 16-20. Subjects will be provided with a subject diary to document daily recordings of home dosing. In the morning of Day 21, subjects will bring their bottle of RBT and bottle of CAB for observed dosing in the unit and safety assessments as an outpatient visit. Following these procedures, subjects will be discharged with their supply of CAB and RBT and instructed to take their daily doses of study medications at home in the mornings of Days 22 through 25. On Day 26, subjects will return to the unit for a pre-dose PK collection and observed dosing as an outpatient visit and then be discharged home. On Day 27, subjects will be re-admitted to the unit for a pre-dose PK collection, observed dosing, and safety assessments then remain in the unit overnight. In the morning of Day 28 following an overnight fast of at least 6 hours, subjects will receive a single dose of RBT and a single dose of CAB in the unit with serial CAB PK samples collected pre-dose and through 24 hours after dosing up to Day 29. Subjects will be discharged from the unit on Day 29 after the final assessment is completed. Subjects will complete a follow-up visit ~ 10-14 days after the last 30 mg oral dose of CAB.

At the follow-up visit, laboratory safety assessments (including pregnancy test for females of childbearing potential) will be performed, and vital signs together with a 12-lead ECG will be obtained.

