10.4.1.1. Treatment States for AE, SAE and Concomitant Medications Data

Treatment State	Definition
Screening	AE(SAE or conmed) Start Date/Time < Study Treatment Start Date/Time. Based on the protocol, these AEs and concomitant medications prior to dosing will not be collected in database, and only record in the source document, but SAE will be captured on the dataset
Treatment A	If AE (SAE or conmed) onset date/time is on or after Period 1 treatment start date/time & before Period 2 treatment date/time Study Period 1 Treatment Start Date/Time ≤ AE Start Date/Time < Study Period 2 Treatment Date/Time]
Treatment B	If AE (SAE or conmed) onset date/time is on or after Period 2 treatment start date/time & before Study Conclusion date/time Study Period 2 Treatment Start Date/Time ≤ AE Start Date/Time < Study follow-up visit Date/Time]
Follow-up	All unsolved AEs (SAE or conmed) during the follow-up will be associated with the treatment from Period 2, and no AEs (SAE or conmed) will be report under the follow-up
Onset Time Since First Dose (Days)	If Treatment Start Date/Time > AE Onset Date/Time = AE Onset Date - Treatment Start Date If Treatment Start Date/Time ≤ AE Onset Date/Time = AE Onset Date - Treatment Start Date +1 Missing otherwise
Duration (Days)	AE Resolution Date – AE Onset Date + 1
Drug-related	If relationship is marked 'YES' on eCRF

NOTES:

- If the study treatment stop date is missing then the AE will be considered to be On-Treatment.

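### The rule for a missing AE start day ignores the Period 2 start, so partially dated combination-period AEs can be counted under CAB alone, never the reverse

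*SAP*

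**What the plan says.** SAP 10.7.2.1 anticipates incomplete AE dates: "The eCRF allows for the possibility of partial dates (i.e., only month and year) to be recorded for AE start and end dates". For a missing start day the rule is "First of the month will be used unless this is before the start date of study treatment", in which case the treatment start date is substituted. The stated purpose is narrow: "the following conventions will be applied for calculating the time to onset and the duration of the event". The same bullet then adds a consequence for treatment state: "hence the event is considered On-treatment as per Appendix 4: Treatment States and Phases".

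Appendix 4 contains the attribution rule, in SAP 10.4.1.1. Treatment A applies "If AE (SAE or conmed) onset date/time is on or after Period 1 treatment start date/time & before Period 2 treatment date/time". Treatment B applies "If AE (SAE or conmed) onset date/time is on or after Period 2 treatment start date/time & before Study Conclusion date/time", and the formula in that row closes the window at the follow-up visit.

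Protocol 4.2 fixes the boundary: "On Day 15 following the completion of the required Day 14 safety assessments and PK collection, subjects will proceed to Period 2". It also says there is no washout, and puts the follow-up visit about 10 to 14 days after the last CAB dose on Day 28, which is Day 38 to 42.

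Neither document says what to do with a partial date whose month contains both Period 1 and Period 2 days. SAP 10.7.2 separately rules out imputation of missing safety data, which does not sit well with the AE date rule directly beneath it.

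**The concern.** Flooring the imputed date at the start of study treatment works where there is one treatment. Here two 14-day periods run back to back, and the date that separates them is the Period 2 start, which the rule never mentions. The first of the month, or Day 1 if later, will often fall before Day 15 even when the event began after rifabutin was added.

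Take a subject who starts on 1 July and has an AE on 20 July, which is Day 20, recorded only as July. The imputed date is 1 July. Onset becomes Day 1 instead of Day 20 and, if that date goes through SAP 10.4.1.1, the event is counted under CAB alone.

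Tolerability of CAB alone and with rifabutin is a secondary objective, and SAP Tables 2.3 and 2.4 summarise all AEs and drug-related AEs by treatment. An error that only ever moves events away from the regimen with the added drug makes that regimen look better tolerated than it was. With 12 to 15 subjects, one subject's event is 1/15 = 6.7 to 1/12 = 8.3 percentage points.

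**Working it through.** The plan states no figure on this point, so there is none to reproduce.

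**Inputs from the documents**
- Imputed date = the later of the first of the recorded month and Day 1 (SAP 10.7.2.1).
- Treatment A if onset is before the Period 2 start, otherwise B (SAP 10.4.1.1).
- Period 2 starts on Day 15; last dose on Day 28; follow-up on Day 38-42 (Protocol 4.2).

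**Assumptions, not in the documents**
- The imputed date is the one used for the A/B split.
- Day 1 is uniform over a four-year calendar of 1461 dates.
- True onset is uniform over the window considered.
- An imputed date on Day 15 itself counts as B.

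**Direction.** The true onset is on or after the first of its own month and, for an on-treatment event, on or after Day 1. The imputed date therefore cannot be later than the true onset. A true Period 1 event stays before Day 15 and remains in A; a true Period 2 event can move to A. Enumeration agrees: 0 of 1461 x 14 Period 1 cases moved to B. This result does not depend on the uniformity assumptions.

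**Size.** For onset on study day t falling on day d of the month, the first of that month is study day t - d + 1. The event goes to A when t - d + 1 < 15, that is, when d >= t - 13. With an average month of 1461/48 = 30.44 days, the share moved is 1 - mean(t - 14)/30.44.

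| True onset | mean(t - 14) | Share moved to A |
|---|---|---|
| Days 15-28 | 7.5 | 1 - 7.5/30.44 = 75.4% |
| Days 15-38 | 12.5 | 1 - 12.5/30.44 = 58.9% |
| Days 15-42 | 14.5 | 1 - 14.5/30.44 = 52.4% |
| Days 15-21 | 4 | 86.9% |
| Days 22-28 | 11 | 63.9% |
| Days 29-42 | 21.5 | 29.4% |

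Enumerating all start dates gives the same values.

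**Spread by start date.** For one Day 1 date the share runs from 0%, when Day 15 is the first of a month, to 100%. For onset on Days 15-28 it is 100% for 54% of start dates and above half for 74%. Over Days 15-42 it is above half for only 51%. Subjects starting around the 11th to the 18th of a month average below half even for Days 15-28.

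**After the change proposed below.** If nothing recorded resolves the period, the move from B to A falls to 0%. The move from A to B rises from 0% to at most 75.4% of partially dated Period 1 AEs, because the Day 15 month contains that share of Period 1 onset days. Every event resolved by a stop date or other record lowers that ceiling.

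**The case against.** The strongest reply is textual. SAP 10.7.2.1 limits the imputation to time to onset and duration, SAP 10.4.1 defines the on-treatment state as both periods together, and SAP 10.4.1.1 does not mention imputed dates. On that reading the reference to Appendix 4 settles only whether the event was before or during treatment, and the plan has no A/B rule for partial dates. A reader might otherwise infer that the SAP expressly places such events under CAB alone; it does not say so. What remains is that the A/B rule needs an onset date, the imputed one is the only one provided, and the text sends the event to the appendix where the split is made. On either reading the derived onset is never later than the true onset and will often be earlier.

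A reader might also take 75% as the size of the problem. That figure applies to Days 15-28 only. The SAP's Treatment B window runs to the follow-up visit, where the average is 52-59%, and all these figures apply only to AEs with no start day.

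Such AEs should be few. Subjects are in the unit across the boundary from Day 13 to Day 15, attend on Days 21 and 26, and return for Days 27-29. Listings show partial dates as captured, the investigator's causality judgement is independent of the imputation, and safety is summarised descriptively. All of this stands and keeps the point minor. Against it, most Period 2 doses are taken at home, where onset dates depend on recall, and a reader of the by-treatment tables alone could not see a misplaced event.

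**Conclusion.** The point holds as a minor defect. The floor in SAP 10.7.2.1 is at the wrong date for a two-period study. If the imputed date feeds the split in SAP 10.4.1.1, which the text implies but does not state, any misplacement runs from the combination to CAB alone. Under uniform start dates and uniform onset the average share moved is 75% for onset during rifabutin dosing and 52-59% over the full Treatment B window, with 0-100% by start date.

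The by-treatment AE summaries and the derived onset times are exposed; the dates shown in the listings and the causality flags are not. The documents do not give the frequency of partial dates, so they do not support a claim that the safety comparison will be materially biased. The primary pharmacokinetic analysis is untouched.

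**What to change.** Amend SAP 10.7.2.1 as follows:

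- When the recorded month includes or follows the Period 2 start, and neither the AE's stop date nor other recorded data place the event in Period 1, impute the later of the first of the month and the Period 2 start date.
- Use that date for both treatment assignment and time to onset, and say so in SAP 10.4.1.1.
- Where the visit at which the AE was first reported is available, use it to settle the period. The documents do not say that it is captured, so the rule should not depend on it.
- Flag imputed events in the AE listing.
- Reconcile with SAP 10.7.2, for example by naming AE dates as the exception to its statement on imputation.

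The cost is a few sentences in the SAP and a small change to the AE derivation. The downside is that some unresolved Period 1 AEs may be counted under the combination, including any first mentioned only after Day 15. That is also a one-way error, but in the conservative direction for the added drug, and the flag lets a reader see how many events it concerns.

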4.6.1. Risk Assessment-Cabotegravir

Potential Risk of Clinical Significance	Summary of Data/Rationale for Risk	Mitigation Strategy
Investigational Product (IP) Cabotegravir		

Drug Induced Liver Injury (DILI)
	
A small proportion of participants in the CAB program to date (total exposure approximately 1289 as of 01 October 2016) have developed transaminitis (elevated liver transaminases characterised by predominant alanine aminotransferase [ALT] elevation). In some of these participants, transient transaminitis was explained by acute hepatitis C infection whilst a small number of others did not have alternative explanations, suggesting a mild form of DILI without hepatic dysfunction which resolved upon withdrawal of treatment with CAB.
 
Of the five participants with possible or probable cases of DILI identified in Phase 2 studies, four participants were receiving oral CAB and one participant developed probable DILI following CAB LA or Placebo LA administration.
	
 • Exclusion criteria as described in Section 5.2 will prohibit participants with significant liver impairment based on prior medical history and screening liver chemistry including transaminases (ALT and Aspartate aminotransferase [AST]). • Liver transaminases (ALT and AST) will be closely monitored throughout this study (refer to Time & Events Table) and the liver chemistry stopping criteria will be adopted as described in Section 5.4.2 of this protocol. • All instances of liver transaminase elevations of Grade 2 and above will be followed to resolution. Participants withdrawn from CAB treatment due to meeting liver chemistry stopping criteria will be regularly monitored both clinically and using liver chemistries to determine progress towards resolution of the liver event.

Potential Risk of Clinical Significance	Summary of Data/Rationale for Risk	Mitigation Strategy
Investigational Product (IP) Cabotegravir		

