7.3.1.1. Time period and Frequency for collecting AE and SAE information

- Any SAEs assessed as related to study participation (e.g., protocol-mandated procedures, invasive tests, or change in existing therapy) or related to a GSK product will be recorded from the time a subject consents to participate in the study up to and including any follow-up contact.
- AEs will be collected from the start of Study Treatment until the follow-up contact. Refer to Section 7.3.1.3.
- Medical occurrences that begin prior to the start of study treatment but after obtaining informed consent may be recorded on the Medical History/Current Medical Conditions section of the CRF.
- All SAEs will be recorded and reported to GSK within 24 hours, as indicated in [Appendix 4](#).

- Investigators are not obligated to actively seek AEs or SAEs in former study subjects. However, if the investigator learns of any SAE, including a death, at any time after a subject has been discharged from the study, and he/she considers the event reasonably related to the study treatment or study participation, the investigator must promptly notify GSK.

NOTE: The method of recording, evaluating and assessing causality of AEs and SAEs plus procedures for completing and transmitting SAE reports to GSK are provided in [Appendix 4](#).

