9.2. Sample Size Considerations

9.2.1. Sample Size Assumptions

The sample size of 15 to obtain 12 evaluable subjects was chosen based on an expected withdrawal rate of approximately 20% and the within-subject variability of CAB, to address the objectives of the study.

The within-subject variations in PK parameters from previous tablet administration in CAB studies [GlaxoSmithKline Document Number [RM2008/00856/00](#), ITZ111839 and GlaxoSmithKline Document Number [2011N122099_01](#), LAI116181] were in the range of 6.7-7.8%, and 6.9-11.4%, for the CAB PK parameters AUC(0- τ)/AUC(0- ∞) and Cmax respectively.

Based on a within-subject coefficient of variation (CV_w) of 11.4% and a sample size of 12 evaluable subjects, it is estimated that the half width of the 90% confidence interval for the treatment difference on log-scale will be within 8.3% of the point estimate for AUC(0- τ) and Cmax. If the point estimate of the ratio of geometric means is 1, then 90% confidence interval will be approximately (0.92, 1.09)

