12.7. Appendix 7: Toxicity Management

ANEMIA

Grade 1 (mild) hemoglobin decrease:

Any hemoglobin decrease meeting the definition of Grade 1 must be repeated with the following additional tests:

1. peripheral blood smear
2. indirect bilirubin (abnormal if increased >50% from baseline)
3. haptoglobin (abnormal if ≤ 25 mg/dL)
4. reticulocyte count (abnormal if $\geq 4\%$)

If the additional tests are within the normal range, subjects may continue study medication. If one or more of the additional tests is abnormal or suggestive of hemolytic anemia as specified above, subjects will permanently discontinue study medication and be withdrawn from the trial. Subjects should be followed up until resolution of anemia.

Grade 2 (moderate) hemoglobin decrease:

Any hemoglobin decrease meeting the definition of Grade 2 must be repeated with the following additional tests:

5. peripheral blood smear
6. indirect bilirubin (abnormal if increased >50% from baseline)
7. haptoglobin (abnormal if ≤ 25 mg/dL)
8. reticulocyte count (abnormal if $\geq 4\%$)

If the additional tests are within the normal range, subjects may continue study medication. If one or more of the additional tests is abnormal or suggestive of hemolytic anemia as specified above, subjects will permanently discontinue study medication and be withdrawn from the trial. Consultation with a Hematologist should be considered. Subjects should be followed up until resolution of anemia.

Grade 3 (severe) or Grade 4 (potentially life threatening) hemoglobin decrease:

Any hemoglobin decrease meeting the definition of Grade 3 or 4 must be repeated with the following additional tests:

9. peripheral blood smear
10. indirect bilirubin
11. haptoglobin
12. reticulocyte count

Subjects will permanently discontinue study medication and be withdrawn from the trial. Consultation with a Hematologist should be considered. Subjects should be followed up until resolution of anemia.

TOTAL BILIRUBIN ELEVATION

Grade 1 (mild) bilirubin elevation (1.1 - 1.5 times ULN) or Grade 2 (moderate - 1.6-2.5 times ULN):

Any bilirubin value above the upper limit of normal must be repeated and fractionated (direct and indirect bilirubin). Subjects may continue study medication. Subjects should be followed up until resolution (return to baseline) of elevation.

Grade 3 (severe – 2.6-5.0 times ULN) or 4 (life-threatening - > 5.0 times ULN) bilirubin elevation:

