2.3. Study Design

Overview of Study Design and Key Features				
Table 1 Study Design				
Subjects	Screening Period	Period 1 Days 1 – 14	Period 2 Days 15 - 28	Follow-up
N=15	Within 30 Days of Day 1	Treatment A	Treatment B	~10-14 days after last dose of CAB

 • Treatment A = CAB 30 mg once daily x 14 days • Treatment B = RBT 300 mg once daily + CAB 30 mg once daily x 14 days 				
Design Features	This study is a phase I, single-center, open label, fixed-sequence, 2-period crossover study in healthy adults.			

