10.11.4. Safety Tables

Safety Tables					
No.	Population	IDSL / TST ID / Example Shell	Title	Programming Notes	Deliverable [Priority]
Adverse Events					
2.1.	Safety	LAI117010/ Table 2.1	Summary of Exposure Data	By subject and treatment	SAC
2.2.	Safety	LAI117010/ Table 2.2	Relationship of Adverse Event System Organ Classes, Preferred Terms, and Verbatim Text		SAC
2.3.	Safety	LAI117010/ Table 2.3	Summary of All Adverse Events by Treatment		SAC
2.4.	Safety	LAI117010/ Table 2.4	Summary of Drug-Related Adverse Events by Treatment		SAC
2.5.	Safety	LAI117010/ Table 2.5	Listing of Serious Adverse Events	By subject and treatment.	SAC
2.6.	Safety	LAI117010/ Table 2.6	Listing of Adverse Events Leading to Permanent Discontinuation of Study Drug or Withdrawal from Study	By subject and treatment	SAC
Labs					
2.7.	Safety	LAI117010/ Table 2.7	Listing of Reference Ranges for Clinical Laboratory Tests		SAC
2.8.	Safety	LAI117010/ Table 2.8	Summary of Clinical Haematology Laboratory Data by Treatment and Time		SAC
2.9.	Safety	LAI117010/ Table 2.9	Summary of Clinical Chemistry Laboratory Data by Treatment and Time		SAC
2.10.	Safety	LAI117010/ Table 2.10	Summary of Treatment Emergent Grade 2 or Higher Lab Abnormalities by Treatment	Summary of Treatment Emergent Lab toxicity only.	SAC
2.11.	Safety	LAI117010/ Table 2.11	Listing of Treatment Emergent Grade 2 or Higher Lab Abnormalities	By subject and treatment	SAC
2.12.	Safety	CP_LB5	Summary of All Urinalysis Data		SAC

Safety Tables					
No.	Population	IDSL / TST ID / Example Shell	Title	Programming Notes	Deliverable [Priority]
Vital Signs					
2.13.	Safety	LAI117010/ Table 2.13	Summary of Vital Signs by Treatment and Time	Include BP and HR only.	SAC
2.14.	Safety	LAI117010/ Table 2.14	Summary of Change from baseline in Vital Signs by Treatment and Time	Include BP and HR only.	SAC
2.15.	Safety	LAI117010/ Table 2.15	Listing of Vital Signs for Subjects with Abnormalities of Potential Clinical Importance	By subject and treatment	SAC
ECGs					
2.16.	Safety	LAI117010/ Table 2.16	Summary of ECG Findings		SAC
2.17.	Safety	LAI117010/ Table 2.17	Summary of ECG Values by Treatment and Time		SAC
2.18.	Safety	LAI117010/ Table 2.18	Summary of Change from Baseline in ECG Values by Treatment and Time		SAC
2.19.	Safety	LAI117010/ Table 2.19	Summary of Category of QTc Data by Treatment and Time		SAC
2.20.	Safety	LAI117010/ Table 2.20	Summary of Category of QTc Change from Baseline by Treatment and Time		SAC

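### A missing AE stop day is capped at the end of treatment although AEs are collected until the follow-up contact, so some derived durations come out zero, negative or too short

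*SAP*

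**What the plan says.** Three rules meet here.

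- **Imputation.** SAP 10.7.2.1 covers AE dates recorded as month and year only. A missing stop day becomes the last day of the month, "unless this is after the stop date of study treatment; in this case the study treatment stop date will be used". The section applies its conventions to time to onset and duration. Completely missing dates are left missing, and listings show partial dates as they were captured.
- **Duration.** SAP 10.4.1.1 defines it as "AE Resolution Date – AE Onset Date + 1".
- **Collection window.** Protocol 7.3.1.1 states that "AEs will be collected from the start of Study Treatment until the follow-up contact". SAP 2.3 places that visit about "10-14 days after last dose of CAB". SAP 10.4.1.1 also assigns AEs that start up to the follow-up visit to Treatment B, so the SAP itself expects onsets after the last dose.

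The protocol follows some events past the end of treatment. Protocol 4.6.1 says "All instances of liver transaminase elevations of Grade 2 and above will be followed to resolution". Protocol 12.7, for subjects who discontinue because of a fall in haemoglobin, says "Subjects should be followed up until resolution of anemia".

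**The concern.** The cap assumes that no AE ends after treatment ends, while the collection window runs 10 to 14 days longer. Neither document keeps the imputed stop date from falling before a known onset date or before the recorded stop month.

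The effect takes two forms. A zero or negative duration is impossible and would probably be noticed. A shortened duration looks plausible and would not be. The second form bears most on AEs that lead to stopping: under this rule such an AE cannot outlast the last dose. SAP 10.11.4 gives these events their own display ("Listing of Adverse Events Leading to Permanent Discontinuation of Study Drug or Withdrawal from Study").

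What is at stake is one derived safety variable. Neither the primary PK comparison nor the AE incidence tables depend on it.

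**Working it through.** The documents give no AE-duration figure to reproduce, so the check applies the stated rules to dates.

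**Inputs**
- Last dose for a completer: Day 28 (Protocol 4.2).
- Follow-up contact: 28 + 10 = Day 38 to 28 + 14 = Day 42 (SAP 2.3).
- Imputed stop = the earlier of (last day of stop month, treatment stop date) (SAP 10.7.2.1).
- Duration = stop - onset + 1 (SAP 10.4.1.1).

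**1. Complete onset date after Day 28, stop day missing.** The last day of the stop month is never before the true stop, which is after Day 28. The cap therefore always applies, whatever the calendar dates, and duration = 28 - onset day + 1 = 29 - onset day.

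| Onset day | Imputed duration (days) |
|---|---|
| 29 | 0 |
| 37 (day before a Day 38 contact) | -8 |
| 41 (day before a Day 42 contact) | -12 |

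An onset on the contact day itself, before the visit, gives one day lower: -9 or -13.

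**2. Onset on treatment, resolution after the last dose.** The stop is cut at the last dose, so the error is resolution day minus 28: a loss of 1 to 10 days (contact Day 38) or 1 to 14 days (contact Day 42), for AEs that resolve by the contact.
- Day 26 to Day 36: true 36 - 26 + 1 = 11 days; imputed 28 - 26 + 1 = 3 days.
- Illustrative early stop, last dose Day 21, AE from Day 20 to Day 30: true 11 days; imputed 21 - 20 + 1 = 2 days.

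**3. Wrong month.** First dose 1 July, last dose 28 July, AE from 4 August to 'August': the imputed stop is 28 July and the duration is -6 days. Over 365 first-dose dates and every stop day from Day 29 to the contact, taken as equally likely (assumption), the imputed stop falls in an earlier month than the recorded one in 660 of 3,650 cases (18.1%, contact Day 38) or 1,260 of 5,110 (24.7%, contact Day 42).

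**4. Current rule against the corrected rule.** The corrected rule uses the last day of the recorded stop month, capped at the contact, and never before onset or the first day of that month. The grid is 365 first-dose dates, onset from Day 1 to the day before contact, and stop from Day 29 (or onset, if later) to contact, all equally likely (assumption).

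| | Contact Day 38 | Contact Day 42 |
|---|---|---|
| Cases | 121,910 | 181,040 |
| Mean absolute error, current rule | 5.7 days (all too short) | 7.9 days (all too short) |
| Mean absolute error, corrected rule | 3.8 days (never too short) | 5.1 days (never too short) |
| Largest overstatement, corrected rule | 9 days | 13 days |
| Corrected rule: duration 0 or less, or wrong month | 0 | 0 |

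**The case against.** The strongest reply is that nothing planned depends on this variable. The displays in SAP Table 6 and Appendix 11 cover incidence, relatedness, seriousness, withdrawal and liver events, and none is titled as a duration display. Listings keep partial dates as captured, so a reader of the source dates is not misled. The trigger is also narrow: a stop month known but its day unknown, in a study of about 15 subjects with database cleaning before analysis. AEs still ongoing at the contact have no stop date and are not imputed. All of this stands, and it is why the point is minor. It does not rescue the rule: the SAP chose to define duration and to pre-specify the imputation that feeds it, and that imputation gives impossible values.

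A second reply also stands in part: the corrected rule is not unbiased. It replaces understatement with overstatement about two-thirds as large (3.8 against 5.7 days; 5.1 against 7.9). What it gains is a smaller error and no impossible values.

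Three stronger readings are tempting and are not supported.
- A reader might infer that AE attribution to Treatment A or B is distorted. SAP 10.7.2.1 confines the conventions to time to onset and duration, and its only link to treatment state is to On-treatment, which pools both periods.
- A reader might take 18.1% to 24.7% as the share of AEs affected. Those figures apply only once a partial stop date after Day 28 exists; the documents give no frequency for that.
- A reader might treat the withdrawal rate in Protocol 9.2.1 as such a frequency. It covers withdrawal for any reason and says nothing about partial AE dates.

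**Conclusion.** The stop-day rule is wrong as written, and the point is minor. For a completer with a complete onset date after Day 28 and a month-only stop date, the zero or negative duration follows from the SAP's own rules with no assumption about calendar dates. The range is 0 to about -8 (contact Day 38) or 0 to about -12 (contact Day 42). The lower ends are not hard limits, since an onset on the contact day takes one day more and the visit timing is itself approximate. AEs that run past the last dose are cut at it. The wrong-month shares and mean errors rest on the equal-likelihood assumption and describe the rule, not the expected number of affected AEs, which is unknown. Whether duration is printed in any listing cannot be settled from the documents, because the listing shells are not shown.

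**What to change.** Replace the missing-stop-day sentence in SAP 10.7.2.1 with this rule: use the last day of the recorded stop month, capped at the study conclusion or follow-up contact date, and never earlier than the AE onset date or the first day of the recorded stop month. The last floor is needed for events followed to resolution after the contact, where a cap alone could place the stop in an earlier month.

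In the example above (onset 4 August, stop 'August'), the new rule gives a stop of 7 August and 4 days if the contact is on Day 38, or 11 August and 8 days if it is on Day 42, instead of -6.

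The cost is one sentence and one derivation rule, with no new data or assessments. The downside is the average overstatement of 3.8 or 5.1 days shown above, which is in the same direction as the month-end convention that the SAP already uses.
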